6.3 COVARIATES AND STRATIFICATION FACTORS

The potential influences of baseline patient characteristics such as age, gender, C-peptide level following a MMTT at study entry on the primary and secondary endpoints will be evaluated in a multivariate model to see whether they have an effect on the treatment vs. placebo comparison.

7 HANDLING OF MISSING VALUES

7.1 MISSING DATES

In compliance with TrialNet standards, if the day of the month is missing for any date used in a calculation, the 15 of the month will be used to replace the missing date unless the calculation results in a negative time duration (e.g., date of resolution cannot be prior to date of onset; if replacing resolution date with the 15 of the month results in a negative duration, the resolution date will be set to the onset date). In this case, the date resulting in 0 time duration will be used. If the start date is missing for an AE, the AE is considered to be treatment emergent unless the collection date is prior to the treatment start date.

7.2 MISSING VALUES for AUC

For the calculation of AUC following a MMTT, no values will be imputed for missing data; however if a single timed value is unavailable the calculation will proceed with the remaining known timed values. AUC is calcuted using the trapezoidal technique based on observed values and actual measurement times. If more than one timed value is missing the AUC will be considered missing.

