### 4.6 Metabolic Monitoring

Individuals will undergo a 2-hour MMTT for C-peptide measurements to determine eligibility for the study at screening. The investigational drug is not anticipated to have any metabolic effect in subjects with established T1D. However, repeat MMTT procedures will be done at months 1, 3, 6, and 12 to evaluate potential adverse effect of therapy on insulin secretion. HbA1c, blood glucose, and total daily insulin dose will also be monitored according to the schedule of assessments.

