6.2 SECONDARY ENDPOINTS

 $\Delta AUC_{0-2h,C-peptide,MMTT}$; Relative change in the area under the plasma C-peptide concentration-time curve from time 0 to 2 hours during MMTT from baseline to 3 months (visit 14) between groups. The comparison will be blinded until the last patient has been followed for 12 months.

Additional Outcomes and Analyses

It is the aim to perform additional analysis to get information of the appearance and disappearance of Plasmid DNA and RNA at various time points during the trials conduct period:

- Plasmid DNA and RNA concentrations at selected time points before and from 1 hour to up to 48 hours after the first dose (Visits 0-2, days 0-2)
- Plasmid DNA and RNA concentrations before second dose (Visit 3, day 7 +/- 1 day)
- Plasmid DNA and RNA concentrations before dose 5 (Visit 6, day 28 +/- 1 day)
- Plasmid DNA and RNA concentrations before dose 8 (Visit 9, day 49 +/- 1 day)

• Plasmid DNA and RNA concentrations at selected time points after last dose (Visit 14, day 84 +/- 3 days; Visit 15, day 120 +/- 14 days; Visit 16, day 180 +/- 14 days; and Visit 17, day 365 +/- 14 days)

Additional analysis of the impact of study drug on metabolic outcomes (Section 5.4) will be determined at 1-, 3-, 6-, and 12-months following treatment including analysis of changes of these parameters from baseline.

Target Engagement, Mechanistic Outcomes and Exploratory Analysis

The primary time period for evaluation of target engagement and mechanistic outcomes will be accumulated data through visit #14.

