8.2.3 MMTT ANALYSES

Acceleration of beta cell destruction due to immune activation is a potential risk, which will be monitored through $AUC_{0-2h,C-peptide,MMTT}$. The plasma C-peptide concentration-time curve from time 0 to 2 hours during MMTT obtained at the end-of dosing day 85 for the treatment and placebo arms will be compared for each cohort (N=3 placebo, and N=9 treated) and at the end of the study by cohort (i.e., pooling the placebo treated patients, N=12 placebo, N=9 treated in each cohort).

The MMTT analysis will be conducted on a transformed scale using the function log (1+ $AUC_{0-2h,C-peptide,MMTT}$). This provides better normal distributional behavior by the test statistic. The comparison between the two treatment arms will be based on a test of the difference between the means.

When an adjustment for covariates is desired, the comparison will be made using a Wald test of treatment effect in an ANCOVA model adjusting for gender, baseline age, and baseline.

The study has a 72%-87% power to detect a 50% or less treatment ratio when the coefficient of variation (CoV) ranges from 0.38 to 0.31. This is based upon historical data derived from recent onset patients (REF). Should the observed CoV be larger, there would be a corresponding reduction in power to detect a 50% treatment ratio or a corresponding decrease in the detectable treatment ratio to retain 80% or greater power. The power to detect a 50% or less treatment ratio at the end of the study (using the pooled placebo patients) is uniformly >90%.

Additionally, using a published methodology, the observed transformed AUC C-peptide can be compared visually with the expected AUC C-peptide calculated from TrialNet historical data from untreated recent onset patients.

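### SAP 7.2 does not exempt the 0- and 120-minute samples from its one-missing-value rule, so a shortened C-peptide area is analysed as a full AUC from 0 to 2 hours

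*SAP*

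**What the plan says.** SAP 7.2 governs missing values in the MMTT area. Four statements there act together:

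- On imputation: "no values will be imputed for missing data".
- On one missing sample: "if a single timed value is unavailable the calculation will proceed with the remaining known timed values".
- On the method: "AUC is calcuted using the trapezoidal technique based on observed values and actual measurement times".
- On two or more missing samples: "If more than one timed value is missing the AUC will be considered missing".

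SAP 6.2 defines the secondary endpoint as the relative change in the C-peptide area "from time 0 to 2 hours during MMTT from baseline to 3 months (visit 14) between groups". SAP 8.2.3 says the arms "will be compared for each cohort (N=3 placebo, and N=9 treated"), and again at the end of the study with the 12 placebo participants pooled. Protocol 8.2 and 8.5 use the same 0-to-2-hour area. Protocol 4.6 and 5.4 describe a 2-hour test at screening and at months 1, 3, 6 and 12. Neither document lists the sampling times within the test.

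**The concern.** A trapezoidal area runs from the first to the last observed sample. If an interior value is absent, the rule joins its neighbours and still covers the full period. If the first or last value is absent, there is nothing to join to, and the end interval drops out. SAP 7.2 treats both cases alike, so the shortened area goes into the analysis under the full-interval name. Because C-peptide concentrations are positive, the error is always downward for that test.

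The direction of the consequence depends on the visit. A shortened visit 14 area looks like loss of insulin secretion. A shortened screening area hides loss in the relative-change endpoint and in a baseline-adjusted model, though not in an unadjusted comparison of post-dose means. Protocol 4.9.2 also gives the escalation reviewers the available MMTT areas by individual participant. If the same rule is used for those, one shortened curve can mislead there too.

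Blinding gives no reason to expect lost samples to favour one arm. The worry is a single case in a small group, chiefly the per-cohort comparison with 3 placebo participants.

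**Working it through.** **Step 1. Does any other text correct the rule?** No. Neither document requires both end samples, rescales the area by the observed duration, extrapolates to 0 or 120 minutes, or flags a shortened curve. SAP 7.3 deals with PK/PD concentrations, not the MMTT. Using actual measurement times handles a late draw, not an absent one. The shortening therefore follows from the text for any sampling schedule.

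**Step 2. Size for one participant (assumed inputs).** Assume samples at 0, 15, 30, 60, 90 and 120 minutes and six illustrative curves. AUC = Σ (tᵢ₊₁ − tᵢ)(cᵢ + cᵢ₊₁)/2. The entries are the area with one sample missing divided by the full area.

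| Curve at 0/15/30/60/90/120 min | 120 missing | 0 missing |
|---|---|---|
| flat | 0.750 | 0.875 |
| .25/.40/.55/.75/.80/.75 | 0.702 | 0.938 |
| .30/.40/.55/.80/.90/.85 | 0.689 | 0.938 |
| .30/.50/.70/.80/.70/.55 | 0.762 | 0.924 |
| .20/.27/.36/.52/.66/.75 | 0.649 | 0.942 |
| .20/.22/.26/.32/.34/.32 | 0.719 | 0.911 |

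Any single interior sample missing gives 0.962 to 1.004. The loss is therefore 24-35% for the last sample, 6-12.5% for the first and 0-4% for an interior one. With 15-minute spacing throughout, losing the last sample costs 11-18% (ratios 0.819-0.888). If a second pre-meal sample serves as time 0, losing the 0-minute sample costs about nothing.

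**Step 3. Relative change for one participant, taking a 25% shortening.**

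- Visit 14 shortened, no true change: 0.75 − 1 = −25%.
- Baseline shortened, no true change: 1/0.75 − 1 = +33%.
- Baseline shortened, true 25% loss: 0.75/0.75 − 1 = 0%.

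**Step 4. Reproduce the plan's power.** Protocol 8.5 and SAP 8.2.3 state 72%-87% for a 50% ratio at a CoV of 0.38 to 0.31. Use a two-sample t-test on log AUC (the scale in Protocol 8.5), noncentral t, and two-sided alpha 0.05 (assumed; none is stated).

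- SD = √ln(1 + CoV²) = 0.367 and 0.303.
- Noncentrality = ln 2 / [SD √(1/3 + 1/9)] = 2.83 and 3.43, with 10 degrees of freedom.
- Power = 72.3% and 87.1%, which matches.
- For 12 vs 9: 98.2% and 99.8%, consistent with the stated figure above 90%.

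**Step 5. Effect of one value shortened by 25% (mean shift only, true ratio 0.50).** A placebo case gives a ratio of 0.5/0.75^(1/n), where n is the placebo number. An active case gives 0.5 × 0.75^(1/9).

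| Situation | Apparent ratio | Power, CoV 0.38 / 0.31 |
|---|---|---|
| 3 vs 9, complete | 0.50 | 72.3% / 87.1% |
| 3 vs 9, one placebo shortened | 0.550 | 59.6% / 76.0% |
| 3 vs 9, one active shortened | 0.484 | 76.1% / 89.8% |
| 2 vs 9, that placebo test set to missing | 0.50 | 57.7% / 74.1% |
| 3 vs 8, that active test set to missing | 0.50 | 70.0% / 85.2% |
| 12 vs 9, one placebo shortened | 0.512 | 97.5% / 99.7% |
| 11 vs 9, that placebo test set to missing | 0.50 | 97.8% / 99.8% |

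**Step 6. The SAP's own scale.** SAP 8.2.3 analyses log(1 + AUC). For areas A from 0.2 to 100, the share of a 50% effect removed by one shortened placebo value out of 3 is {[ln(1+A) − ln(1+0.75A)]/3} / [ln(1+A) − ln(1+0.5A)], about 14-16%. On plain logs it is [ln(1/0.75)/3]/ln 2 = 14%. The transformation does not remove the problem.

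**The case against.** The literal reading of SAP 7.2 is hard to dispute; the objections concern importance.

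- **Frequency.** The documents give no rate of lost end samples, so no expected impact can be stated. Every group figure above supposes that exactly one loss occurs. This stands.
- **Assumed schedule and curves.** The percentages depend on them. This also stands, and other plausible schedules give smaller errors.
- **Arm.** With 9 of 12 participants on active drug, a random loss is three times likelier there, and power then rises (76-90%). That is correct, but it comes from an apparent ratio of 0.484 where the truth is 0.50. The bias has changed direction, not gone away.
- **Limited consequence.** The MMTT comparison is secondary, the interruption criteria in Protocol 4.10 contain no C-peptide trigger, and SAP 6.2 keeps the visit 14 comparison blinded until the last participant has 12 months of follow-up. Repeat tests allow a cross-check, and the pooled comparison barely moves. All of this lowers the stakes without making the value correct.
- **Deleting tests costs information.** True: in the 3-placebo comparison, power with the test removed (58-74%) is no better than with the shortened value (60-76%). The gain is removal of bias, not power.
- **Time-averaging.** Dividing by the observed duration would keep the participant. On the six curves it leaves an error of about −13% to +8%. It is a workable alternative, but neither document specifies it.

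**Conclusion.** The concern holds. SAP 7.2, as written, yields an area over less than two hours whenever the first or last sample is the one missing, and SAP 6.2 and 8.2.3 analyse it as the full area. That conclusion needs no assumption about the schedule.

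The size does. On the assumed schedule and curves, the error in one participant's AUC is 24-35% for a lost last sample and 6-12.5% for a lost first sample. At group level it matters for the 3 vs 9 comparison (ratio 0.50 read as 0.55 or 0.484, depending on the arm) and hardly at all when placebo is pooled (0.512 for one placebo case, power still 97% or more). The group figures also assume one affected test with a 25% shortening, alpha 0.05 two-sided and no effect of the outlying value on the SD. The overall impact cannot be given because the frequency is unknown. The rule should be corrected, but it does not threaten the primary safety analysis.

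**What to change.** In SAP 7.2:

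1. List the planned MMTT sampling times, including any second pre-meal sample.
2. Limit the one-missing tolerance to interior samples.
3. Set the AUC to missing if the 120-minute sample is absent, or if the 0-minute sample is absent and no other pre-meal sample can stand as time 0.
4. Apply this equally to screening and every follow-up test, and report the number of tests affected by arm.

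If the team prefers to keep such tests by time-averaging over the observed interval, the SAP should say so and name the residual error. Either choice should be fixed before unblinding, so that nobody has to decide about an odd curve once the arms are known.

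The cost is one sentence, one programming condition and the loss of each affected test. One lost placebo test leaves 58-74% power in a per-cohort comparison and about 98% or more in the pooled one. One lost active test leaves 70-85% per cohort.

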7.3 MISSING PK/PD VALUES

Concentrations below the limit of quantification

In all data presentations (except listings), concentrations below the limit of quantification (BLQ) will be set to zero. In listings, BLQ values will be reported as "<LLQ", where LLQ will be replaced with the value for the lower limit of quantification.

Deviations, missing concentrations, and anomalous values

In summary tables, statistics will be calculated having set concentrations to missing if 1 of the following cases is true:

- 1. A concentration has been noted as ND (i.e., not done) or NS (i.e., no sample);
- 2. A deviation in sampling time is of sufficient concern or a concentration has been flagged anomalous by the pharmacokineticist.

8 STATISTICAL METHODOLOGY AND STATISTICAL ANALYSES

8.1 STATISTICAL METHODS

8.1.1 Analyses of Continuous Data

Descriptive statistics, including the mean, standard deviation, median, minimum, and maximum values will be provided.

8.1.2 Analyses of Categorical Data

The number and percentage of patients in each category will be provided for categorical variable.

8.2 STATISTICAL ANALYSES

8.2.1 Standard Analyses

Descriptive statistics will be used to summarize study conduct, patient disposition, baseline characteristics, and treatment administration/compliance.

Study Conduct and Patient Disposition - an accounting of the study patients will be tabulated for the FA population. Patients not meeting eligibility criteria will be identified. Patients not completing the study will be listed along with the reason for their premature discontinuation. Reasons for premature discontinuation will be summarized.

Baseline Characteristics - patient characteristics such as age, gender, race, ethnicity, duration of disease will be provided in frequency tables and descriptive statistics for quantitative variables.

Treatment Administration/Compliance - Administration of study medication will be presented for the SA population, by medication administered within each treatment group and will be described in terms of the total number of doses administered, the median (range) of doses administered, dose modifications, dose interruptions, dose delays due to adverse event and other reasons for dose modifications, interruptions or delays.

8.2.2 SAFETY ANALYSES

Safety data will be analyzed in the SA population. Adverse events and select laboratory values (e.g., hematology, blood chemistry and others) may also be summarized by the treatment arms. Only grade 2 or higher AEs are to be reported for visits 16 and 17, as per protocol.

On-Treatment Adverse Events

An overall summary of AEs as described above will be provided. AEs will be summarized for all doses and also by dose. The most commonly reported AEs (5% or more of patients) will also be summarized by preferred term. A summary of AEs by preferred term and maximum CTCAE grade, as well the grouped maximum CTCAE grade group (Grade 1-2 vs. Grade 3-4 vs. Grade 5) will be presented. Only patients who experience AEs during the AE reporting period will be listed.

Treatment Related Adverse Events

Treatment-related AEs are those judged by the Investigator to be at least possibly related to the study drugs [with a cause related to study drug as indicated on the case report form (CRF)] or for which relatedness is recorded as "unknown" by the Investigator. Similar summaries as noted for AEs will be provided for treatment related AEs.

Serious Adverse Events and Death

On-treatment SAEs and treatment-related SAEs will be summarized by MedDRA SOC and preferred term. Patients who experienced a SAE during the SAE reporting period will be listed for all randomized patients. The number and percentage of patients who experienced any serious treatment - emergent SAE will be summarized for all doses. A summary of SAEs by preferred term, maximum CTCAE grade and grade group will be presented.

Deaths will be summarized by time period (on-treatment vs. during follow-up) and cause of death. Deaths that occurred on or after first dose of study medication and within 28 days after the last dose of study medication are defined as on-treatment deaths. A listing of death data will also be provided and it will include all deaths that occurred during the reporting period for deaths which starts from the signing of the informed consent to the end of the follow up period for death.

Concomitant medications/Follow-up systemic therapy - All medications received during the treatment period will be considered as concomitant medications and will be coded by WHO medical dictionary. Patients who received concomitant medications will be listed. Follow-up systemic therapy for primary diagnosis will be summarized by categories of follow-therapy and will be listed for each patient.

8.2.3 MMTT ANALYSES

Acceleration of beta cell destruction due to immune activation is a potential risk, which will be monitored through $AUC_{0-2h,C-peptide,MMTT}$. The plasma C-peptide concentration-time curve from time 0 to 2 hours during MMTT obtained at the end-of dosing day 85 for the treatment and placebo arms will be compared for each cohort (N=3 placebo, and N=9 treated) and at the end of the study by cohort (i.e., pooling the placebo treated patients, N=12 placebo, N=9 treated in each cohort).

The MMTT analysis will be conducted on a transformed scale using the function log (1+ $AUC_{0-2h,C-peptide,MMTT}$). This provides better normal distributional behavior by the test statistic. The comparison between the two treatment arms will be based on a test of the difference between the means.

When an adjustment for covariates is desired, the comparison will be made using a Wald test of treatment effect in an ANCOVA model adjusting for gender, baseline age, and baseline.

The study has a 72%-87% power to detect a 50% or less treatment ratio when the coefficient of variation (CoV) ranges from 0.38 to 0.31. This is based upon historical data derived from recent onset patients (REF). Should the observed CoV be larger, there would be a corresponding reduction in power to detect a 50% treatment ratio or a corresponding decrease in the detectable treatment ratio to retain 80% or greater power. The power to detect a 50% or less treatment ratio at the end of the study (using the pooled placebo patients) is uniformly >90%.

Additionally, using a published methodology, the observed transformed AUC C-peptide can be compared visually with the expected AUC C-peptide calculated from TrialNet historical data from untreated recent onset patients.

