#### 8.5 Statistical Considerations for Assessment of Worsening of Insulin Secretion.

Acceleration of beta cell destruction due to immune activation is a potential risk, which will be monitored through AUC0-2h,C-peptide,MMTT. The log-transformed area under the plasma C-peptide concentration-time curve from time 0 to 2 hours during MMTT obtained at the end-of dosing day 84 for the treatment and placebo arms will be compared for each cohort (N=3 placebo, and N=9 treated) and at the end of the study by cohort (i.e., pooling the placebo treated patients, N=12 placebo, N=9 treated in each cohort). The study has a 72%-87% power to detect a 50% or less treatment ratio when the coefficient of variation (CoV) ranges from 0.38 to 0.31. This is based upon historical data derived from recent onset patients (51). Should the observed CoV be larger, there would be a corresponding reduction in power to detect a 50% treatment ratio or a corresponding decrease in the detectable treatment ratio to retain 80% or greater power. The power to detect a 50% or less treatment ratio at the end of the study (using the pooled placebo patients) is uniformly >90%.

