2.2 STUDY OBJECTIVES

Primary Objective:

To investigate the safety and tolerability of ascending subcutaneous weekly doses of NNC0361-0041 plasmid in patients with T1D.

Secondary Objectives:

To investigate effect on target engagement, immune response, and beta cell function following ascending subcutaneous weekly doses of NNC0361-0041 plasmid in patients with T1D.

3. Population Definitions

Up to 12 patients will be randomized to treatment vs. placebo within each of 4 cohorts. The goal is to have a minimum of 9 patients within each cohort to have received at least 10 of the planned 12 treatment doses.

Randomized:	Met eligibility criteria and randomly assigned to a treatment arm without consideration of actually receiving
	treatment.
Randomized and partially	Met eligibility criteria, randomly assigned to a treatment
treated:	arm and received at least 1 – 9 doses.
Randomized and treated:	Met eligibility criteria, randomly assigned to a treatment
	arm and received at least 10 doses.
Pretreatment period	From signing of informed consent until 1 st treatment

On-treatment period	From 1 st treatment through visit 15 (or 5 weeks after last treatment for subjects not receiving all injections)
Follow-up period	From visit 15 (or 5 weeks after last treatment) through visit 17

Up to 2 additional individuals within each cohort may be enrolled to complete the target 9 patients randomized and treated to account for those who are randomized and partially treated.

4. SAFETY and INSULIN SECRETION ANALYSES

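### C-peptide is tested only cohort by cohort; adding an all-active contrast, a dose trend and a shared error variance would detect losses short of halving better

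*SAP*

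**What the plan says.** SAP 2.2 gives the secondary objective as "To investigate effect on target engagement, immune response, and beta cell function following ascending subcutaneous weekly doses". For C-peptide, SAP 8.2.3 and Protocol 8.5 plan two comparisons of the MMTT AUC: the arms "will be compared for each cohort (N=3 placebo, and N=9 treated) and at the end of the study by cohort". Each cohort's 9 treated participants are set against that cohort's 3 placebo participants, and then, at the end of the study, against the placebo groups of all cohorts combined ("pooling the placebo treated patients, N=12 placebo, N=9 treated in each cohort").

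The SAP's main method is unadjusted: "The comparison between the two treatment arms will be based on a test of the difference between the means". An ANCOVA on gender, age and baseline may be used when adjustment is wanted. No rule says when that is, or to which comparison it applies.

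On power: "The study has a 72%-87% power to detect a 50% or less treatment ratio", when "the coefficient of variation (CoV) ranges from 0.38 to 0.31". For the pooled-placebo comparison the power is put above 90%. Neither document gives alpha or sidedness.

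For adverse events, SAP 8.2.2 plans summaries over all doses as well as by dose. C-peptide has no counterpart. SAP 6.3 mentions a multivariate model of treatment against placebo but does not define the treatment group.

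**The concern.** Accelerated beta-cell loss is a risk that the protocol names (6.2.1, 8.5), and SAP 6.1 plans no formal test for the primary endpoint. The C-peptide comparison therefore carries much of the inferential weight on harm. As specified, each test estimates its own error variance from 12 or 21 people. No test asks whether the product as a class lowers C-peptide, and none asks whether C-peptide falls as dose rises. A moderate loss shared across doses, or one that grows with dose, is what pooled and ordered contrasts detect best.

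**Working it through.** **Inputs.** Group sizes, CoV 0.38 to 0.31 and ratio 0.50 are from SAP 8.2.3 and Protocol 8.5. Allocation of 36 active and 12 placebo is from SAP 2.1. Assumed: two-sided 5%, log-normal AUC, equal variances, no dropout. Paired results are for CoV 0.38/0.31.

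**Scale.** SD = sqrt(ln(1 + CoV²)) = 0.367/0.303. A ratio of 0.50 is ln 2 = 0.693. A 30% loss is −ln 0.70 = 0.357.

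**Method.** SE = SD × sqrt(1/n1 + 1/n2), and power comes from the noncentral t. The multipliers are 0.667 (9 vs 3), 0.441 (9 vs 12) and 0.333 (36 vs 12).

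**The plan's own figures.**
- 9 vs 3, 10 df: noncentrality 0.693/(0.667 × 0.367) = 2.83, or 3.43 at the lower CoV. Power 72.3%/87.1%, as stated.
- 9 vs 12, 19 df: 98.2%/99.8%, in line with the statement of more than 90%.

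**Shared variance for 9 vs 3.** Four cohorts by two arms leave 48 − 8 = 40 df. Power at ratio 0.50 rises to 79%/92%.

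**30% loss at every dose.**

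| Analysis | Power | Error in the harm direction, no effect |
|---|---|---|
| One 9 vs 3 test | 26%/36% | 2.5% |
| One 9 vs 12 test | 55%/72% | 2.5% |
| Any of four 9 vs 12 tests (simulated, shared placebo) | about 85%/94% | about 8% |
| Any of four, Bonferroni | about 62%/80% | at most 2.5% |
| All active vs placebo, 36 vs 12 | 81%/93% | 2.5% |

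With equal cohort sizes, comparing within cohorts and averaging gives the same 0.333 multiplier. The ratio detectable with 80% power is 0.62/0.67 for 9 vs 12 and 0.70/0.75 for all active.

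**Loss rising evenly with dose rank to 30% at the top dose.** Code placebo 0 and the doses 1 to 4. The sum of squares is 9 × 30 − 90²/48 = 101.25 and the slope is 0.357/4 = 0.089 per rank, so the noncentrality is 0.089 × sqrt(101.25)/0.367 = 2.44 at CoV 0.38. Trend-test power is about 67%/83%, against 55%/72% for the top dose alone vs pooled placebo.

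**30% loss at the top dose only.** The all-active contrast sees 0.357/4 = 0.089. Its power is about 11%/14%, against 55%/72% for the planned top-dose test.

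**ANCOVA with three covariates.** Inside a 12-person cohort, 12 − 5 = 7 df remain and the variance of the treatment effect rises about 1.5-fold on average (simulated covariates, independent of treatment). At ratio 0.50:

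| Share of outcome variance explained (R²) | Power, 9 vs 3 |
|---|---|
| 0 | 54%/70% |
| 0.2 | 63%/78% |
| 0.3 | 69%/83% |
| 0.5 | 81%/92% |

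Break-even with 72%/87% is at R² of about 0.36-0.40. The documents give no R². In 9 vs 12 the same ANCOVA has 95%/99% even at R² = 0. If the Wald test used a normal reference with 7 df, its two-sided error would be about 9.1%.

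**The case against.** The strongest reply is that the plan runs four end-of-study tests. Read together, they flag a uniform 30% loss about as often as the all-active test (85%/94% against 81%/93%). They also flag a rank-ordered loss about as often as the trend test (67%/81% against 67%/83%). That stands as far as detection goes, so a reader should not infer that such losses would probably escape the plan altogether. It is paid for with about 8% false harm signals. For the uniform loss, power falls to 62%/80% once that error is controlled. The documents set no multiplicity rule either way.

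Four further readings are tempting and go too far:
- That the plan discards most of the 48 participants' information. This is true of a single 9 vs 3 test, with 25% of the all-active information (2.25 of 9.0). Each 9 vs 12 test keeps 57% (5.14 of 9.0), and the four together use everyone.
- That the stated power is wrong. It is right for the unadjusted test.
- That the SAP places the ANCOVA inside a 12-person cohort. It does not say where the ANCOVA is fitted.
- That this is the only inferential look at C-peptide. SAP 6.2 also names a between-group relative change to visit 14, and the model in SAP 6.3 might pool active groups, though it does not say so.

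It is also fair that pooling across a 25-fold dose range (1 to 25 mg) can hide harm at one dose.

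**Conclusion.** The point holds as a worthwhile, inexpensive improvement. It is not an error in the stated power. At the planned ratio of 0.50 the end-of-study tests already exceed 98%, so the gain lies in losses short of halving. For a uniform 30% loss, one all-active test gives 81%/93% with controlled error, against 55%/72% per dose. For a dose-ordered loss, the trend gives about 67%/83% against 55%/72% for the top dose alone. A shared variance lifts 9 vs 3 from 72%/87% to 79%/92% before covariate adjustment.

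These figures rest on two-sided 5%, equal variances, no dropout and the plain log scale that reproduces the plan's power. The SAP tests log(1 + AUC), whose effect on power was not assessed. The ANCOVA result depends on an R² that the documents do not give. They also do not say whether the quoted CoV is already baseline-adjusted; if it is, the R² = 0 row applies.

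**What to change.** In SAP 8.2.3:
1. Keep each dose vs pooled placebo, but take all four comparisons from one linear model on every participant with a visit 14 AUC: placebo plus four dose groups, adjusted for baseline, age and sex, with a shared residual variance and a t reference. Add a linear trend over dose rank from this model.
2. From a second model with cohort terms, report all active vs placebo within cohorts, and the 9 vs 3 contrasts. Two models are needed, because cohort terms undo the pooling of placebo.
3. State alpha and sidedness, and label the all-active and trend contrasts as supplementary to the by-dose estimates.
4. State that the ANCOVA is fitted on all participants, not inside a 12-person cohort, and restate power for the contrasts kept.

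The cost is SAP wording and modest programming. SAP 4.2 already places this analysis after all visit 17 assessments, so the timing does not change. There are two downsides: a common variance is assumed across cohorts, and the all-active contrast dilutes harm confined to one dose, so it must not replace the by-dose comparisons.
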